9.6.4 Concomitant Medications

Concomitant medications will be coded using the World Health Organization Drug Dictionary (WHODRUG). A by-subject listing of concomitant medications will include all medications taken during the study. All medications started prior to the administration of the study drug will be included in the data but will be flagged as prior. Only the concomitant medication use will be summarized.

9.7 Interim Analysis

An independent Data and Safety Monitoring Board (DSMB) will monitor the safety of this study. The objectives of the DSMB are to assess drug safety and allow for protocol modification or early stopping due to safety concerns. The DSMB members will include at least one statistician, one clinician of relevant specialty, and one endocrinologist that is familiar with the care of patients with type 2 diabetes. No interim efficacy assessment will be performed.

10 ADMINISTRATIVE CONSIDERATIONS

10.1 Investigators and Study Administrative Structure

Information regarding key personnel involved in the conduct of the study, including names and contact details of participating investigators, monitors, clinical laboratories, technical departments and/or institutions, as well as information on members of additional study committees, will be found in the study files of the study sites.

10.2 Institutional Review Board (IRB) or Independent Ethics Committee (IEC) Approval

This protocol, informed consent document, relevant supporting information, and all types of subject recruitment or advertisement information must be submitted to the IEC or IRB for review and must be approved by The Sponsor and the IEC/IRB before the study is initiated. Any amendments or addenda to the protocol must also be approved by the IEC/IRB prior to implementing changes in the study. The Investigator is responsible for keeping the IEC/IRB apprised of the progress of the study and of any changes made to the protocol as deemed appropriate, but in any case at least once a year. The Investigator must also keep the IEC/IRB informed of any SAEs occurring to subjects under their supervision.

10.3 Ethical Conduct of the Study

The procedures set out in this protocol, pertaining to the conduct, evaluation, and documentation of this study, are designed to ensure that the sponsor and investigator abide by Good Clinical Practice Guidelines and under the guiding principles detailed in the Declaration of Helsinki. The study will also be carried out in keeping with applicable local law(s) and regulation(s). This may include an inspection by the sponsor representatives and/or their designee and/or FDA representatives at any time. The investigator must agree to the inspection of study-related records by the FDA/sponsor representatives, and must allow direct access to source documents to the FDA/sponsor representatives.

The investigator is responsible for complying with the protocol and all appropriate regulations and guidelines governing global clinical research. Additionally, he/she is responsible for ensuring that all participating staff members are adequately trained and competent to perform his/her assigned tasks.

Modifications to the study protocol will not be implemented by either the sponsor or the investigator without agreement by both parties. However, the investigator may implement a deviation form, or a change of, the protocol to eliminate an immediate hazard(s) to the trial subjects without prior IRB/sponsor approval/favorable opinion. As soon as possible, the implemented deviation or change, the reasons for it and if appropriate the proposed protocol amendment should be submitted to the IRB/sponsor.

Any deviations from the protocol must be fully explained and documented by the investigator. The circumstances, action taken and impact of the deviation on the trial must be

communicated by the Principal Investigator to the designated Medical Monitor. Any subsequent actions will be assessed by the designated Medical Monitor and documented.

10.4 Patient Information and Consent

Prior to the beginning of the study, the investigator must have the EC/IRB written approval/favorable opinion of the written Informed Consent Form and any other written information to be provided to subjects. The written approval of the EC/IRB together with the approved subject information/Informed Consent Forms must be filed in the study files. The Informed Consent Form must contain all elements required by the FDA under 21 CFR Part 50 and the International Conference on Harmonisation (ICH) Good Clinical Practices (GCP) Guidelines (E6) in addition to any other elements required by state, local or institutional policy.

Written informed consent must be obtained before any study specific procedure takes place. Participation in the study and date of informed consent given by the subject should be documented appropriately in the subject's files. A copy of the signed informed consent form must be provided to the subject. If applicable, it will be provided in a certified translation in the language understood by the subject if not English. Signed consent forms must remain in each subject's study file and must be available for verification by study monitors at any time.

10.5 Patient Confidentiality

The information obtained during the conduct of this clinical study is confidential, and disclosure to third parties other than those noted below is prohibited. Information obtained during the conduct of this study will be used by The Sponsor in connection with the development of the study drug. The study Investigator is obliged to provide the Sponsor with complete test results and all data developed in this study. Subject-specific information may be provided to other appropriate medical personnel only with the subject's permission. To ensure compliance with current ICH guidelines, data generated by this study must be available for inspection upon request by representatives of national and local health authorities, the Sponsor and the IRB for each study site.

Subject names and other identifiers, such as photographs, audio or videotapes, may not be disclosed in any publication without prior written authorization from the subject.

10.6 Study Monitoring

An authorized Sponsor representative will conduct site visits to inspect study data, subjects' medical records and CRFs in accordance with ICH guidelines, GCPs and the respective local and national government regulations and guidelines.

The Investigator will permit authorized representatives of the Sponsor and the respective national or local health authorities to inspect facilities and records relevant to this study.

10.7 Case Report Forms and Study Records

For each subject consented, a case report form (CRF) will be supplied and maintained by the CRO staff and signed by the investigator or authorized designee to indicate that he/she has reviewed and agrees with the entered data. This also applies to those subjects who fail to complete the trial. The reason a subject is withdrawn must be recorded in the case report form.

Entries made in the CRF must be verifiable against source documents. Source documents are defined as all medical records, medical notes, laboratory results, ECG traces and any additional document other than the CRF that has original subject information contained within it. The diary card that subjects will complete with meal information will be archived but meal information will not be entered in the database. Whether the subject was fasting for 10 hr or not prior to sample collection will be captured in the CRF.

All CRFs and source documents should be completed following GCPs and the CRO's standard operating procedures.

10.8 Protocol Violations/Deviations

Protocol "violations" include deviations from the inclusion and exclusion criteria, concomitant medication restrictions, and any other protocol requirement that results in a significant added risk to the patient or has an impact on the quality of the data collected or the outcome of the study. Protocol violations must be reported to the Ethics Committee or Institutional Review Board in a timely manner. Protocol violations must be reported in the final study report.

A protocol deviation occurs when there is non-adherence to study procedures or schedules, as specified by the protocol, which does not involve inclusion/exclusion criteria or the primary endpoint and which does not place the patient at any added risk or affect the data quality or study outcome. If deviations occur, such as a missed visit or missed sampling window, the investigator must decide whether to proceed, for example, whether or not to complete the visit or sample collection outside of the protocol-defined window. The sponsor's medical monitor must be notified immediately when protocol deviations are discovered so that a decision can be made about the continued participation of the subject in the study.

A departure from the protocol for an individual subject can only be made without the Sponsor approval in the event of an emergency. The nature and reasons for the protocol deviation will be recorded in the CRF and the Principal Investigator must notify the Sponsor.

10.9 Access to Source Documentation

Authorized Sponsor representatives will conduct site visits to inspect study data, subject medical records and CRFs in accordance with ICH guidelines, GCP and the respective local and national government regulations and guidelines.

The Investigator will permit authorized representatives of the Sponsor and the respective national or local health authorities to inspect facilities and records relevant to this study.

Each center will be visited at regular intervals by a monitor to ensure compliance with the study protocol, GCP and legal aspects. This will include on-site checking of the case report forms (CRF) for completeness and clarity, cross-checking with source documents, and clarification of administrative matters.

All CRF data will be entered into a clinical database. Following the correction of any errors, the clinical database will be locked.

10.10 Data Generation and Analysis

For each subject who is randomized to receive study drug, a case report form (CRF) must be maintained by a trial coordinator and signed by the investigator or authorized designee to indicate that he/she has reviewed and agrees with the entered data. This also applies to those subjects who fail to complete the trial. The reason a subject is withdrawn must be recorded in the CRF. Subjects whose eligibility is not confirmed on day 1 are considered screen failure and no CRF will be maintained for those subjects.

Entries made in the CRF must be either verifiable against source documents, or have been directly entered into the CRF, in which case the entry in the CRF will be considered as the source data. Source documents are defined as all medical records, medical notes, laboratory results, ECG traces and any additional document other than the CRF that has original patient information contained within it.

All source documents must be legible. Errors must be lined out and the correction must be made, initialed and dated by the person making the correction.

The Sponsor or designated CRO is responsible for data processing and data query. The investigator or designated staff is responsible for query resolution and data clarification.

10.11 Retention of Data

The study file and all source data should be retained until notification given by the sponsor for destruction. If the investigator withdraws from the trial and relinquishes his/her responsibility for the maintenance and retention of records, he/she must notify the Sponsor in writing so arrangements can be made to properly store the trial materials.

10.12 Publication and Disclosure Policy

All data and results and all intellectual property rights in the data and results derived from the study will be the property of the Sponsor, who may utilize the data in various ways, such as for submission to government regulatory authorities or disclosure to other investigators.

No publication or disclosure of study results will be permitted except as specified in a separate, written agreement between Theracos, Inc. and the investigator. If results of this study are reported in medical journals or at meetings, all subjects' identities will remain confidential.

Appendix 1 Schedule of Events

Visit Number		Screening & Run-in		Primary Efficacy Phase						Extension Phase						
		2	3	4	5	6	7	8	9	10	11	12	13	14	ET	
Time Relative to Randomization Visit (weeks) ¹	-5	-2	0	2	6	12	18	24	36	48	60	72	84	96		
Informed Consent	X															
Screening for I/E criteria	X	X	X													
Medical History	X															
Diet & exercise counseling		X				X		X		X		X				
Diary Review			X	X	X	X	X	X	X	X	X	X	X	X	X	
Discontinue anti-diabetic medication		X														
Randomization			X													
Physical exam	X					X		X		X		X		X	X	
Vital signs	X	X	X	X	X	X	X	X	X	X	X	X	X	X	X	
ECG	X		X					X			X			X	X	
Dispense study medication		X	X		X	X	X	X	X	X	X	X	X			
Blood draw for clinical lab test ²			X	X	X	X	X	X	X	X	X	X	X	X	X	
PK sample				X	X	X	X	X	X	X	X	X	X	X		
Urinalysis ³	X		X	X	X	X	X	X	X	X	X	X	X	X	X	
AE^4			X	X	X	X	X	X	X	X	X	X	X	X	X	
Con Med			X	X	X	X	X	X	X	X	X	X	X	X	X	

Confidential Page 57 of 61

EGT0001442 tablet

Clinical Trial Protocol: THR-1442-C-418

02 February 2011

Screening period may last up to 21 days (V1 to V2), Run-in period is to be 14±3 days (V2 to V3), V3 to V4 window is 14±3 days, all other visit windows are the nominal duration from randomization ± 7 days.

Blood sample for these lab tests at the designated visit:

V1: CBC, electrolytes, BUN, creatinine, Lipids (TG, TC, HDL-C), ALT, AST, bilirubin (total and direct), PT, HbA1c, FPG, TSH, aPTT, Hepatitis Screen (HBsAg, HBcAg, HCV)

V3: CBC, electrolytes, BUN, creatinine, Lipids (TG, TC, HDL-c), ALT, AST, bilirubin (total and direct), HbA1c, FPG

V4: CBC, electrolytes, BUN, creatinine, HbA1c, FPG

V5: CBC, electrolytes, BUN, creatinine, HbA1c, FPG

V6: CBC, electrolytes, BUN, creatinine, Lipids (TG, TC, HDL-c), ALT, AST, bilirubin (total and direct), HbA1c, FPG

V7: CBC, electrolytes, BUN, creatinine, HbA1c, FPG

V8-V14 and ET: CBC, electrolytes, BUN, creatinine, Lipids (TG, TC, HDL-c), ALT, AST, bilirubin (total and direct), HbA1c, FPG

- Clean catch sample to be collected at each visit. If urine is dipstick positive for WBC or blood sample is to be sent for microscopic evaluation and culture. Urine pregnancy test and drug screen on screening (visit 1)
- Adverse events of special interest are specified to be:
 - Cardio- and cerebro- vascular events,
 - Genitourinary infections
 - Increase in creatinine from baseline by 0.5 mg/dL or more
 - Increase in ALT, AST or bilirubin to >3x ULRR

Confidential Page 58 of 61

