7.2.2 Visit 4 – Procedures (week 2)

- The subject must be queried to assess compliance with a minimum of a 10 h fast prior to blood draw to ensure the FPG values can be accurately determined. Only water is permitted. If a subject has not fasted for 10 h, the subject should return within a week after proper fasting.
- Diary and SMBG review
- Vital Signs: blood pressure, pulse, temperature, respiratory rate taken in the sitting position after at least 5 minutes of rest. Blood pressure must be measured twice with at least 3 min apart
- Blood draw for hematology (CBC with platelets, WBC with differential), serum chemistry including FPG, and coagulation as detailed in section 6.7.1
- Urinalysis

- Collect plasma sample for drug exposure verification
- Assess adverse events and record concomitant medications

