9.6.3 Clinical and Laboratory Events and Analyses

Clinical and laboratory metrics are measured at baseline and weeks 2, 6, 12 and 24 during the study. During the treatment extension they are measured every 12 weeks up to a total of 96 weeks. These variables include vital signs (blood pressure, respiration, and temperature), Clinical laboratory (see section 6.7 for a complete list) and ECGs.

Laboratory data will be summarized using Low-Normal-High shift tables. ECG results will be summarized as changes from baseline in intervals. Abnormalities as well as changes from previous assessment will be listed.

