**Table 2: Analysis Visit Windows** 

Scheduled Visit	Target Study Day of Visit	Slotting Intervals
Week -5 (Screening)	-35	<=-25
Week -2	-14	-24 to -4 days
Baseline (Week 0)	1	-3 to 1 days
Week 2	15	2 to 29 days
Week 6	43	30 to 64 days
Week 12	85	65 to 106 days
Week 18	127	107 to 148 days
Week 24	169	149 to 211 days
Week 36	253	212 to 295 days
Week 48	337	296 to 379 days
Week 60	421	380 to 463 days
Week 72	505	464 to 547 days
Week 84	589	548 to 631 days
Week 96 (End of Treatment	673	632 to (last dose date)
Visit)*		
Week 97**	680	>Last dose date + 7 days
1 Week Follow-up Visit**	Last dose date + 7 days	>Last dose date + 7 days

\* Week 96 is the end of treatment visit for those subjects completing the study per protocol. For subjects who withdraw early from active treatment, the end of treatment visit will be assigned to an analysis visit based on the visit slotting algorithm using study day.

For parameters which were not scheduled to be collected at all visits, still use the all-inclusive visit intervals defined for all visits (that is, the visit window table above) to slot records. However, if a value is slotted to a visit unscheduled for a parameter, it will not be summarized except for summaries focusing on extreme values such as laboratory shift tables. These records will also be included in data listings.

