#### **9.2** Labs

### 9.2.1 Hematology, Chemistry and Urinalysis

Laboratory parameters include the following tests: hematology, chemistry, and urinalysis. Established or generally acknowledged methods, normal ranges, and quality control procedures will be supplied by the local and central laboratory for the study records.

Hematology parameters used in summaries include hematocrit, hemoglobin, platelet count, red blood cell (RBC) count, and white blood cell (WBC) count with differential. Chemistry

Final – 22November2011 CONFIDENTIAL Page 27 of 30

parameters (including lipids) used in summaries include albumin, ALT, AST, blood urea nitrogen, calcium, bicarbonate, chloride, direct bilirubin, glucose, magnesium, phosphorus, potassium, sodium, total bilirubin, total protein, uric acid, total cholesterol, LDL cholesterol, HDL cholesterol, triglycerides, and ApoB. Urinalysis parameters used in summaries include appearance, bilirubin, color, glucose, ketones, microscopic examination of sediment, nitrites, occult blood, pH, protein, specific gravity, and urobilinogen.

All laboratory parameters will be summarized for each treatment group, at every assessed time point using descriptive statistics and graphical displays of the means and standard deviations over time. In addition, for hematology and chemistry laboratory parameters, changes from baseline in these quantitative tests will be summarized by treatment group and at every assessed post-baseline time point.

Shift tables will be developed by first classifying the subject laboratory results as low, normal, or high in comparison to the applicable laboratory reference range. The number and percentage of subjects with indicated shifts (low, normal, high) in their results from baseline to each post-baseline assessment will be presented for all hematology, chemistry and applicable urinalysis parameters. All laboratory data will be listed.

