## Table 14.3-2.2 Change from Baseline in Chemistry (Safety Analysis Set)

See table 14.3-2.1 for layout. Use footnote below.

Note: Baseline is defined as the last available assessment on or prior to the first dose of study medication. Source Data: Listing 16.2-9.2

Programming note: use timepoints of Baseline, Week 2, 6, 12, 18, 24, 36, 48, 60, 72, 84, 96, 97 and 1 week follow-up.

<DIRECTORY PATH>PROGRAM NAME Executed: DDMMMYYYY hh:mm Data Extracted: DDMONYYYY

Final - 22November2011 CONFIDENTIAL Page 64 of 106

Table 14.3-2.3 Urinalysis (Safety Analysis Set)

	EGT0001442	Placebo	
	(N=xxx)	(N=xxx)	
Albumin (unit)			
Screening			
n	xxx	xxx	
Mean (SD)	xx.x (xx.xx)	xx.x (xx.xx)	
Median	xx.x	xx.x	
Min, Max	xx, xx	xx, xx	
Week 0			
Urinary Protein			
Screening			
n	xxx (xx.x%)	xxx (xx.x%)	
4	xxx (xx.x%)	xxx (xx.x%)	
5	xxx (xx.x%)	xxx (xx.x%)	
·			

Source Data: Listing 16.2-9.3

Programming note: use timepoints of Screening, Week 0, 2, 6, 12, 18, 24, 36, 48, 60, 72, 84, 96, 97 and 1 week follow-up.

Protocol: THR-1442-C-418 Page x of y

Table 14.3-2.4 Shift in Hematology (Safety Analysis Set)

		EGT0001442			Placebo	
	(N=xxx)		(N=xxx)			
		Baseline			Baseline	
	Low	Normal	High	Low	Normal	High
Lab Test #1 (unit)						
Week 2		n = xxx			n = xxx	
Low	xxx (xx.x%)					
Normal	xxx (xx.x%)					
High	xxx (xx.x%)					
Week 6		n = xxx			n = xxx	
Low	xxx (xx.x%)					
Normal	xxx (xx.x%)					
High	xxx (xx.x%)					

Note: Baseline is defined as the last available assessment on or prior to the first dose of study medication. The number of subjects with a value at baseline and at the specified visit is displayed.

Source Data: Listing 16.2-9.1

Programming note: use all available timepoints per data following order such as Baseline, Week 2, 6, 12, 18, 24, 36, 48, 60, 72, 84, 96, 97 and 1 week follow-up.

Protocol: THR-1442-C-418 Page x of y

Table 14.3-2.5 Shift in Chemistry (Safety Analysis Set)

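### Protocol Section 7 orders liver tests at Weeks 2, 6 and 18, but the visit panels that probably govern omit them, so no post-dose liver test is scheduled until Week 12

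*Protocol*

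**What the plan says.** Protocol 7.2.2 (Week 2) orders "serum chemistry including FPG, and coagulation as detailed in section 6.7.1". Sections 7.2.3 (Week 6) and 7.2.5 (Week 18) use the same words, with no test excluded. The Section 6.7.1 chemistry list includes ALT, AST, total bilirubin and direct bilirubin.

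Protocol Appendix 1 footnote 2 gives a panel for each visit. For Week 2 it is "V4: CBC, electrolytes, BUN, creatinine, HbA1c, FPG", and the V5 and V7 lines list the same tests. For Week 12 it is "V6: CBC, electrolytes, BUN, creatinine, Lipids (TG, TC, HDL-c), ALT, AST, bilirubin (total and direct), HbA1c, FPG". The liver analytes are also named at V1, V3, V8-V14 and early termination. SAP Table 1 footnote 4 leaves them out at the same three visits.

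On timing, Protocol 3.3, 6.7.1 and 6.7.2.1 all refer the reader to Appendix 1. Section 7 presents its own visit lists alongside an appendix, which it calls Appendix A, and does not say which prevails.

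Appendix 1 footnote 4 and SAP Table 1 footnote 7 both name ALT, AST or bilirubin above three times the upper limit as an event of special interest. Protocol 6.9.1 makes such a value a laboratory adverse event.

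SAP 5.4.2 adds a rule for off-schedule data: "if a value is slotted to a visit unscheduled for a parameter, it will not be summarized". It makes an exception for summaries of extreme values, such as shift tables, and keeps the records in the listings.

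**The concern.** The liver event is defined by a laboratory value. A rise without symptoms is found only if the analytes are run, so the test schedule determines how soon it can be found. If the panels are followed, nothing is scheduled from Day 1 to Week 12, or between Weeks 12 and 24. Early-termination tests and tests requested by the investigator could still find a rise sooner.

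Three features of the plan make the early gap worth closing:

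- The other laboratory-defined event in the same list, a creatinine rise of 0.5 mg/dL or more, is covered at every post-dose treatment visit, including V4, V5 and V7. No reason is given for treating the liver event differently.
- Exclusion criterion 7 removes only subjects at or above three times the upper limit. A subject just below the event threshold could be randomized and then have no scheduled liver test for about 12 weeks.
- The clinical summary in Protocol 1.1.2 states dosing durations of no more than 28 days. The untested interval therefore includes the first weeks beyond that exposure.

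If some sites followed Section 7 and others the panels, liver testing would also differ between sites.

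**Working it through.** **Inputs.** Post-dose visits through Week 24 are Weeks 2, 6, 12, 18 and 24 (Days 14, 42, 84, 126 and 168). The window is ±7 days for visits after Week 2 in the protocol, and ±3 days for V3 to V8 in SAP Table 1 footnote 1. The plan states no figure of its own to reproduce.

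**Schedule.**

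| | Panels | Section 7, or panels after the fix |
|---|---|---|
| Weeks with liver tests through Week 24 | 12, 24 | 2, 6, 12, 18, 24 |
| Visits covered | 2 of 5 | 5 of 5 |
| Gaps from Day 1 (weeks) | 12, 12 | 2, 4, 6, 6, 6 |
| Longest gap (weeks) | 12 | 6 |

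The latest in-window date for the first test under the panels is (84 + 7)/7 = 13.0 weeks by the protocol, or (84 + 3)/7 = 12.4 weeks by the SAP. After Week 24 the gaps are 12 weeks on either schedule.

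**Illustration, if the panels are followed.** Assume that onset is uniform over Days 0-168 and that visits fall on the target day. Neither assumption comes from the documents.

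- Mean wait from onset of a persistent rise to the next scheduled test = sum(gap²)/(2 × 168).
  - Panels: (84² + 84²)/336 = 42.0 days.
  - With the fix: (14² + 28² + 3 × 42²)/336 = 18.7 days.
- Chance that a scheduled test falls within a rise lasting d days = sum(min(d, gap))/168.

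| Assumed d | Panels | With the fix |
|---|---|---|
| 14 days | 28/168 = 17% | 70/168 = 42% |
| 28 days | 56/168 = 33% | 126/168 = 75% |
| 42 days | 84/168 = 50% | 168/168 = 100% |

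**Other texts that might settle the schedule.**

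- Protocol 9.6.3 states: "Clinical and laboratory metrics are measured at baseline and weeks 2, 6, 12 and 24 during the study". It covers vital signs, laboratory tests and ECGs together, but Appendix 1 schedules no ECG at Weeks 2, 6 or 12, and the sentence omits Week 18. It is a loose summary and only weak support for liver testing at Weeks 2 and 6.
- The shell for SAP Table 14.3-2.2 says: "use timepoints of Baseline, Week 2, 6, 12, 18, 24, 36, 48, 60, 72, 84, 96, 97 and 1 week follow-up". This is one layout for all chemistry. SAP 9.2.1 says that the "parameters (including lipids) used in summaries include albumin, ALT, AST, blood urea nitrogen", and it goes on to the electrolytes. BUN and electrolytes are on the V4, V5 and V7 panels, so the shell needs Weeks 2, 6 and 18 whether or not liver tests are run.

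**If sites follow Section 7 instead.** The values exist. With SAP Table 1 taken as the schedule, SAP 5.4.2 could remove the Week 2, 6 and 18 liver values from the by-visit change summaries. Shift tables and data listings keep them, and a value above the threshold is an adverse event that reaches the adverse event tables.

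**The case against.** The strongest reply is that the text largely settles the matter. Section 7 points to 6.7.1, which points to Appendix 1 for the schedule; 6.7.2.1 and 3.3 do the same. Section 7's wording also looks like repeated boilerplate: it orders coagulation at every blood-draw visit, while the protocol panels list PT only at V1. The SAP panels were revised after the original protocol (aPTT removed, a serum pregnancy test added, PT at V8 and at V15 or early termination added), and V4, V5 and V7 still carry no liver tests. On this view the omission is deliberate, and the rest is preference about test frequency.

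Most of this stands, and the panels are the likelier governing text. But that reading is the one that produces the 12-week gap, and it leaves Section 7 ordering something else. The panels are not exhaustive (none names albumin, total protein, uric acid or ApoB). Even so, they name the liver tests at other visits and omit them only at these three, so a laboratory could reasonably take that as intended.

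It is also fair that the toxicology findings in Protocol 1.1.1 are gastrointestinal and renal, that 1.1.2 reports no liver event, and that 12-week liver intervals are accepted throughout the extension. These points lower the severity. They do not explain why creatinine is tested at V4, V5 and V7 and the liver analytes are not.

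Finally, the protocol available is the original of 02 February 2011. The SAP of 22 November 2011 refers to versions of April, August and September 2011, so Section 7 may since have changed.

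**Conclusion.** The mismatch is real, and under the likelier reading the first scheduled post-dose liver test is at Week 12, with coverage at 2 of 5 visits through Week 24. It is a low-severity safety-monitoring point and does not affect the primary efficacy analysis.

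A reader might infer three stronger things that the documents do not support:

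- That the documents are evenly split on which schedule applies, with 9.6.3 and the SAP chemistry shell confirming liver tests at these weeks. Three protocol sections point to Appendix 1, and those two texts are weak evidence.
- That liver events would be lost from the analysis. At most, by-visit change summaries at three visits lose values.
- That subjects face a known liver risk that goes untested. No clinical liver signal is reported.

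The schedule counts rest on the text alone. The waiting times and detection percentages are illustrations under assumed onset and duration. The protocol side of the conflict assumes that Section 7 still reads this way in the version in force.

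**What to change.** Add ALT, AST and total and direct bilirubin to the V4, V5 and V7 lines of Protocol Appendix 1 footnote 2 (in the version in force, if Section 7 still reads this way) and of SAP Table 1 footnote 4. The panels then match Section 7 for these analytes, the liver event gets the same visit coverage as the creatinine event, and Weeks 2, 6 and 18 become scheduled visits for them under SAP 5.4.2.

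State in Section 7 that Appendix 1 governs. That settles the remaining differences on lipids and coagulation. Used alone, it would remove the conflict but leave about 12 weeks after first dose without a scheduled liver test.

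Cost: at most 300 × 3 = 900 liver panels (900 × 4 = 3,600 results) on blood already drawn, and none at sites already following Section 7. No visit or draw is added. A few isolated elevations will need repeat testing. The protocol change needs IRB/IEC approval (Protocol 10.2) across about 35 sites in 4 countries (SAP 5.5), so it is best included in an amendment.
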